3. INTERIM ANALYSES

No interim analyses are planned for this study.

4. PATIENT CHARACTERISTICS

4.1. Patient Disposition

The disposition of all randomized patients will be presented. The number of patients in each Analysis Population will be presented overall and by treatment group. In addition, the reason for treatment discontinuation and study discontinuation will be tabulated for the overall population and by treatment group using the list of reasons provided in the eCRF.

4.2. Protocol Violations

A list of protocol violations that could potentially impact the analysis of the study will be determined during the conduct of the study by study team members who are blinded to study treatment being received. The number and percentage of patients with each violation will be tabulated overall and by randomized treatment assignment.

4.3. Demographics and Baseline Assessments

Patient's baseline age, sex, race, height, body weight, body mass index, number of previously failed therapies, and baseline efficacy measures will be summarized using descriptive statistics by treatment arm and overall. These summaries will be based on the Safety population. Patients who are missing measurements of the baseline variable being analyzed will not be included in the summary for that variable.

For the purposes of the Clinical Trial Registry, a summary will be made by age categorized as 49 or younger, 50-64, 65-84, and 85 or older.

Patient height and weight will be collected prior to randomization. Both variables will be reported in metric units (height in cm and weight in kg) and will be summarized as continuous variables along with Body Mass Index (BMI; in kg/m²).

No statistical testing will be performed for comparisons of baseline characteristics.

4.4. Concomitant Medications

Concomitant medications will be defined as medications taken on or after the date of first dose of randomly assigned study treatment. This includes all medications initially taken prior to the date of first dose of randomly assigned study medication but with a stop date that is either missing or after the date of first dose of randomly assigned study medication. Those medications where the stop date is documented as prior to the date of first dose of randomly assigned study medication will be classified as prior medications. The prior medications will not be included in any summary reports.

The number (percent) of patients who receive each concomitant medication, based on the WHODD preferred drug name, will be tabulated. By-patient listings of all concomitant medications, including WHODD preferred drug name, will be prepared.

5. EFFICACY ANALYSES

5.1. Primary Analysis

Efficacy endpoints will be assessed using the ITT population.

The primary treatment effect will be measured as the difference between each active treatment arm and placebo in the percentage of patients with a $\geq 75\%$ improvement from baseline in PASI (PASI 75) at 12 weeks.

A one-sided Fisher's exact test with a 10% type 1 error rate will be used to compare each PRCL-02 treatment arm to placebo. Point estimates for the treatment differences (PRCL minus placebo) will be calculated using a lower 90% exact unconditional confidence interval.

Supporting Analysis of the Primary Endpoint

The primary treatment difference may be analyzed using only those patients with a Week 12 PASI assessment; that is, no imputation made for early withdrawal.

The primary treatment differences may be analyzed using a Cochran-Mantel-Haenszel test, adjusting for the four strata used in the randomization [weight (< 95kg and $\geq 95\text{kg}$), and prior number of failed therapies (< 3 and ≥ 3)] if there are a sufficient number of patients in each cell.

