10.1. Sample Size Determination

Approximately 27 patients will be randomized to each of the 3 treatment arms. The sample size was chosen so that there is at least 80% power to detect an increase in response of 30% or more in any PRCL 02 treatment arm relative to placebo using a 1 sided Fisher's Exact test with a 10% type 1 error rate. This assumes a placebo response of 7.5% and PRCL-02 response of 37.5% in either PRCL-02 treatment arm for the primary end point, based on available clinical data from marketed injectable and oral targeted therapies for psoriasis. The sample size was calculated assuming a 10% drop out of patients in each arm and that drop-outs would be analyzed as non-responders.

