1.3. Sample Size Determination

Approximately 27 patients will be randomized to each of the 3 treatment arms for a total of 81 patients. The sample size was chosen so that there is at least 80% power to detect an increase in response of 30% or more for the primary objective (percentage of patients reaching a PASI 75 at week 12) in any PRCL-02 treatment arm relative to placebo using a one-sided Fisher's Exact test with a 10% type 1 error rate. This assumes a placebo response of 7.5% and PRCL-02 response of 37.5% in either PRCL-02 treatment arm for the primary end point, based on available clinical data from marketed injectable and oral targeted therapies for psoriasis. The sample size was calculated assuming a 10% drop out of patients in each arm and that drop-outs would be analyzed as non-responders.

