2.7. Handling of Dropouts and Missing Data

Dates

Imputation of missing or partial dates is not expected, but if a complete date is required for calculations, the following algorithms will be applied:

- For the start date:
 - If year, month, and day are missing then use the minimum of the patient's first visit date or the consent date.
 - If either only month or month and day are missing then use January 1.
 - If only day is missing, impute the first day of the month.

- For the end date:
 - If year, month, and day are missing then use the patient's last visit date.
 - If either only month or month and day are missing then use December 31.
 - If only day is missing then use the last day of the month.
 - Do not expand the record past the patient's last visit.

The original missing or partial date, the imputed complete date, and the indicator variable that indicates which dates were imputed will be retained in the database.

PASI and sPGA Response

Patients whose response to treatment cannot be determined due to missing data (including early withdrawal) will be considered non-responders in the analyses.

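### Efficiency point, not an error: replacing the one-sided 10% Fisher test by Boschloo's exact test at the same level would add about 3 to 4 points of power per dose with the same 81 patients

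*SAP*

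**What the plan says.** SAP 5.1 sets the primary test of PASI 75 at Week 12: "A one-sided Fisher's exact test with a 10% type 1 error rate will be used to compare each PRCL-02 treatment arm to placebo". Protocol 10.3.3.1 says the same. Beside the test, SAP 5.1 reports the treatment difference "using a lower 90% exact unconditional confidence interval".

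The design inputs are in SAP 1.3, and Protocol 10.1 agrees with them:

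- Size: "Approximately 27 patients will be randomized to each of the 3 treatment arms for a total of 81 patients".
- Rates: "This assumes a placebo response of 7.5% and PRCL-02 response of 37.5% in either PRCL-02 treatment arm for the primary end point".
- Target: "The sample size was chosen so that there is at least 80% power to detect an increase in response of 30% or more".
- Drop-out: "The sample size was calculated assuming a 10% drop out of patients in each arm and that drop-outs would be analyzed as non-responders".

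SAP 2.7 carries the drop-out rule into the analysis: "Patients whose response to treatment cannot be determined due to missing data (including early withdrawal) will be considered non-responders in the analyses". SAP 2.8 plans no multiplicity adjustment. SAP 5.3 and Protocol 10.3.3.3 analyse PASI 90 in the same way as PASI 75. Neither document gives the error rate that the Fisher test actually attains.

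**The concern.** Fisher's test conditions on the total number of responders in the two arms. When few responders are expected, each total allows only a few outcomes, and the test stops well short of its nominal level. The sponsor accepted a one-sided 10% risk for a small proof-of-concept comparison, and much of that risk may go unused at a 7.5% placebo rate. If another exact test holds the same 10% ceiling and rejects more often under a real effect, the plan gives up some power that would need no extra patients.

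**Working it through.** **Inputs.** 27 per arm; 7.5% vs 37.5%; one-sided 10%; 10% drop-out counted as non-response (SAP 1.3, 2.7, 5.1). Drop-out dilutes the rates to 0.9 × 7.5% = 6.75% and 0.9 × 37.5% = 33.75%.

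**Method.** Let x be placebo responders and y active responders.

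- Fisher p(x, y) = P(Y ≥ y | x + y), the hypergeometric tail; reject if p ≤ 0.10.
- Power or size = sum of Bin(x; 27, π₀) × Bin(y; 27, π₁) over the rejected cells of the 28 × 28 outcome table; for size, π₀ = π₁.
- Boschloo orders tables by the Fisher p-value and rejects up to the largest cut-off whose maximum size over all common rates (grid 0.001 to 0.999) is at most 0.10. At 27 vs 27 that cut-off is a Fisher p of 0.1355.

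**The plan's own figure first.** Fisher power is 88.2% at 7.5% vs 37.5%, 84.2% at the diluted rates, and 85.3% with 24 completers per arm (27 × 0.9 = 24.3). The continuity-corrected formula gives 23 per arm, and 23/0.9 = 25.6, so 26 after drop-out. The promise of at least 80% is met on every footing, and 27 is a reasonable size for this test.

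**Fisher against Boschloo at 27 vs 27, per comparison.**

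| Scenario (placebo vs active) | Fisher | Boschloo |
|---|---|---|
| Size, common rate 7.5% | 3.1% | 5.7% |
| Maximum size, any common rate | 6.7% | 9.7% |
| Power, 7.5% vs 37.5% | 88.2% | 91.5% |
| Power, 6.75% vs 33.75% | 84.2% | 88.0% |
| Power, true 20-point effect 7.5% vs 27.5%, diluted to 6.75% vs 24.75% | 60.0% | 66.4% |

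**Why Boschloo cannot lose.** The Fisher region has size at most 10% for every margin, hence at most 10% unconditionally. The Boschloo cut-off is therefore never below 0.10, and its region contains Fisher's. At 27 vs 27 no rejected cell is lost and 16 are gained.

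**What changes in practice.** With 0/27 placebo responders Fisher needs 4 active responders and Boschloo 3. By hand, the Fisher p for 3/27 vs 0/27 is C(27,3)/C(54,3) = 2925/24804 = 0.118; the Boschloo p is 0.070. With 2/27 placebo responders, about the expected count (27 × 0.075 = 2.0), Fisher needs 7 and Boschloo 6; at 6 vs 2 the p-values are 0.125 and 0.079. With 1 or 3 placebo responders the two tests need the same count (5 and 8).

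**In patients.** At the diluted rates Fisher reaches 87.8% with 30 per arm, so matching Boschloo's 88.0% would take about 3 × 3 = 9 more patients.

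**PASI 90.** The documents give no rates, so these are assumptions. The gain is about 16 points at 15% active vs 1% placebo (53% to 69%), about 8 at 20% vs 2%, and about 4 at 25% vs 1% or 2%.

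**The price.** Two doses share one placebo arm. The chance of at least one false positive is the sum over x of Bin(x; 27, π)[1 − (1 − r(x))²], where r(x) is the chance that one dose is rejected given x. At 7.5% it rises from 5.9% to 10.0%; its maximum over all rates rises from 11.5% to 16.4%.

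**The case against.** The sponsor can fairly say that nothing here is wrong. For an exact test 10% is an upper bound, and Fisher respects it. The sample size was chosen for this test, so its conservatism is already paid for in the 27 per arm. Boschloo does not reach 10% at the planned placebo rate either. All of this stands. A reader might infer from the 3.1% that the plan misstates its error rate, or that the trial is underpowered. The documents support neither: they name a level, not an attained size, and their power statement holds.

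A reader might also infer that Fisher's conservatism buys nothing. That goes too far, because it partly offsets the absence of adjustment for two doses in SAP 2.8. It is not a designed protection, but it would shrink with the switch.

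The gain is also modest. If success on at least one dose is what counts and both doses work, power goes from 94.0% to 96.2% at the diluted rates, about 2 points. Some newly significant results are small against the 30-point design effect: 3/27 vs 0/27 is 11 points and 6/27 vs 2/27 is 15. Whether to call those positive is the sponsor's choice.

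Finally, the unconditional limit in SAP 5.1 is closer in kind to Boschloo than to Fisher. It does not guarantee that test and limit agree, because the SAP does not state the statistic behind the interval.

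**Conclusion.** The point holds as an inexpensive gain in efficiency. At 27 per arm and the planned rates, Boschloo's test adds 3.3 points of per-dose power without drop-out (91.5 − 88.2) and about 3.9 with it. For a true 20-point effect the gain is 6.4 points (66.4 − 60.0). It stays within the 10% level the sponsor set for each comparison. That it is never less powerful than Fisher follows from its construction at any arm sizes. The exact figures rest on 27 analysed per arm, on the response rates in SAP 1.3, and on drop-out that is equal across arms and counted as failure. The PASI 90 gains rest on assumed rates and concern an exploratory endpoint. Whether the extra power is worth a higher two-dose false-positive chance is for the sponsor to decide openly.

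**What to change.** Before unblinding:

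1. In SAP 5.1 and Protocol 10.3.3.1, name Boschloo's exact unconditional test, one-sided 10%, for each PRCL-02 dose against placebo. Use it for PASI 90 as well (SAP 5.3, Protocol 10.3.3.3).
2. State that it is computed at the realised ITT arm sizes. Enrolment is approximate and the ITT set in SAP 2.3 requires a Week 1 PASI, so the cut-off should not be fixed at 27 vs 27.
3. Keep the Fisher p-value as a supportive result.
4. Keep the sample size and the 80% power statement; both remain true.
5. Confirm or revise SAP 2.8 in the same step, naming the two dose comparisons and stating the rise from 5.9% to 10.0% (worst case 11.5% to 16.4%).

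The cost is a few sentences and a small validated program. No patients, visits or data are added. The SAP states that it supersedes the protocol's statistical sections; the sponsor should judge whether a new primary test is a principal feature that needs an amendment under Protocol 10.3.1.

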5.2. Secondary Analyses

Safety/tolerability and PK analyses are described in Section 6 and Section 7, respectively.

5.3. Exploratory Analyses

The percentage of patients with a $\geq 90\%$ improvement from baseline in PASI (PASI 90) at 12 weeks will be analyzed similarly to PASI 75. PASI 75 and PASI 90 will be summarized at each scheduled visit.

Observed values of the PASI score and subscores, the sPGA score, and the change and percent change from baseline to each scheduled visit will be summarized using descriptive statistics and the treatment groups compared using analysis of variance methods.

The quantitative secondary efficacy endpoints will be assessed by analyzing the change from baseline to the 12-week time point using PROC MIXED to model the difference in the Week 12 change from baseline score between treatment groups and to handle missing assessments. The change from baseline to each scheduled post-baseline visit will be estimated using repeated measures mixed models assuming data are missing at random, with covariates for baseline and visit. The lower 95% confidence limit of the difference in mean scores at Week 12 (PRCL minus Placebo) will be estimated from the mixed model. The effects of baseline scores and treatment will be allowed to vary across visits. The following example SAS code will be used, for assessments at Weeks 1, 2, 4, 8, and 12. For patients who withdraw prior to Week 12, data from the early termination visit will be used as the next visit's assessment; for example, if a patient's last scheduled assessment is at Week 4, the early termination data will be included in the analysis as Week 8.

```
proc mixed;
  class visit treatment patient;
  model endpoint=week*baseline week*treatment;
  repeated week / type=vc subject=patient;
  random patient;
run;
```

In addition, plots of each least squares mean (\pm standard error) for the scores by scheduled visit will be created

If the data appear non-Normal or if a reasonable variance-covariance structure cannot be fit to the data, the treatment comparisons will be made using Wilcoxon Rank-Sum tests at each visit using the observed data.

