1. INTRODUCTION AND OBJECTIVES

1.1. Introduction

Study PRCL-POC is a multicenter, randomized, double-blinded, placebo controlled, multiple oral dose parallel design study of PRCL-02 in patients with moderate to severe chronic plaque psoriasis. Clinical evaluations are at pre-treatment, and at Day 1, Weeks 1, 2, 4, 8, 12, 14, 16, 18, and 20 after randomization.

The purpose of this statistical analysis plan (SAP) is to describe the analysis variables and statistical procedures that will be used to analyze and report the results from PRCL-POC: “A Phase 2a Study to Evaluate Safety, Tolerability, and Efficacy of PRCL-02 in Patients with Moderate to Severe Chronic Plaque Psoriasis.”

This SAP is based on the protocol PRCL-POC, which was approved on 16 July 2018.

Some of the analyses detailed here may be more explicit or in some aspects different from those stated in the protocol. In case of differences, this SAP supersedes the statistical sections in the protocol.

Changes to the protocol that impact the design, the data collected, or the statistical methods and that occur after the finalization of this SAP may require amendment of the approved SAP. Similarly, changes to the planned analysis variables and/or statistical methods described in the approved SAP may also require amendment of the SAP.

The formats for the tables, listings, and figures described in this SAP are provided in a companion document. Changes to the formats of these reports that are decided after the finalization of the SAP will not require an amendment. In addition, any additional supportive or exploratory analyses requested after SAP approval will not require amendment of the SAP. These additional analyses will be described in the clinical study report (CSR).

See the study protocol for details about the study design, procedures, and schedule of assessments and see the electronic case report form (eCRF) for details about variables collected and their possible values.

The time and events schedule for this study is provided in Section 10.

EMB Statistical Solutions, LLC will have responsibility for performing these analyses.

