2.13. Computation of Questionnaire Scores

Psoriasis Area and Severity Index (PASI)

The PASI scores the severity of disease on a scale from 0 to 72 (where a score of 72 indicates extreme disease severity) by combining assessments of the extent of body surface involvement (A) in the head, trunk, arms, and legs together with the severity of desquamation (D), erythema (E), and plaque induration (I). Values for the extent of body surface involvement and severity are classified according to Table 3.

Table 3. PASI Scoring

Degree of Severity	Value
None	0
Slight	1
Moderate	2
Marked	3
Very Marked	4
Surface area involved	Value
None	0
< 10%	1
10-29%	2
30-49%	3
50-69%	4
70-89%	5
90-100%	6

The PASI subscore for each region is calculated as $(D+E+I)*A$. The Total PASI score is then calculated as $0.1*(\text{Head Score}) + 0.3*(\text{Trunk Score}) + 0.2*(\text{Arms Score}) + 0.4*(\text{Legs Score})$.

The PASI subscores will not be computed if any element of the equation is missing. The total score will not be computed if any subscore is missing.

Static Physicians Global Assessment (sPGA)

The sPGA defines the severity of disease (an average of the investigator's perception of induration, erythema, and scaling) from clear (score=0) to severe (score=5). Patients were to enter the trial with at least a score of 3 at screening and at randomization; therefore, patients with a post-baseline score less than 3 will be considered responders.

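### For continuous PASI and sPGA the SAP reports the confidence limit on the wrong side of the difference, and its mixed-model code uses a visit variable it never declares

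*SAP*

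**What the plan says.** SAP 5.3 (Exploratory Analyses) plans a repeated-measures mixed model for change from baseline in the quantitative efficacy scores at Weeks 1, 2, 4, 8 and 12. The interval statement is: "The lower 95% confidence limit of the difference in mean scores at Week 12 (PRCL minus Placebo) will be estimated from the mixed model". The model is described in these words: "The effects of baseline scores and treatment will be allowed to vary across visits".

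The SAS code printed below that text, which the SAP calls an example but also commits to using, declares "class visit treatment patient" and then specifies "model endpoint=week*baseline week*treatment". Its REPEATED statement is also indexed by `week`.

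SAP 2.13 fixes the direction of both scores: PASI is "on a scale from 0 to 72 (where a score of 72 indicates extreme disease severity", and sPGA runs "from clear (score=0) to severe (score=5". Higher is worse in both cases.

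For contrast, SAP 5.1 says of the PASI 75 response rates: "Point estimates for the treatment differences (PRCL minus placebo) will be calculated using a lower 90% exact unconditional confidence interval". Protocol 10.3.1 sets a one-sided 10% level for all tests of treatment effects, and SAP 1.1 adds: "In case of differences, this SAP supersedes the statistical sections in the protocol".

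**The concern.** A lower limit for PRCL minus placebo is the right side for a response rate, where more is better. SAP 5.3 uses the same side for scores where less is better. A programmer who follows the sentence would report a number that is almost always negative, whether or not the drug works. It is also the only interval the SAP specifies for the continuous PASI and sPGA comparisons, which serve the exploratory objective of describing clinical response over time.

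The code is a separate fault in the same section. `visit` is declared and never used again; `week` is used and never declared. The text needs time to be a classification variable, so that each visit has its own baseline slope and its own treatment effect. The code does not make it one.

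The stakes are limited to how an exploratory result is computed and reported.

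**Working it through.** No figure stated in the plan is in dispute. The sample size was reproduced for completeness. Exact enumeration of the one-sided 10% Fisher test at 27 per arm gives 88.2% power for 7.5% versus 37.5%. With 10% dropouts counted as non-responders, the rates become 0.9 × 7.5% = 6.75% and 0.9 × 37.5% = 33.75%, and power is 84.2%. The plan's claim of at least 80% holds, and nothing below changes it.

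**Step 1: direction.** Let D be the mean change on PRCL minus the mean change on placebo, with change = post minus baseline. Higher scores are worse (SAP 2.13), so benefit means D < 0. Evidence of benefit needs the upper limit of D below zero. A lower limit above zero would be evidence of harm.

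**Step 2: how often each limit falls below zero.** Work in standard-error units, so no SD is needed. Let d be the true difference (negative = benefit), with a normal approximation:

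- P(lower limit < 0) = Φ(z − d)
- P(upper limit < 0) = Φ(−d − z)
- z = 1.645 for a one-sided 95% limit and 1.2816 for a one-sided 90% limit

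The illustrative benefit is 1.2816 + 0.8416 = 2.123 SE, the size that a one-sided 10% test detects with 80% power.

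| True difference d | Lower 95% below 0 | Upper 95% below 0 | Upper 90% below 0 |
|---|---|---|---|
| 0 (no effect) | Φ(1.645) = 95% | Φ(−1.645) = 5% | Φ(−1.282) = 10% |
| −2.123 (benefit) | Φ(3.768) = 99.99% | Φ(0.478) = 68% | Φ(0.842) = 80% |
| +1 (drug worse) | Φ(0.645) = 74% | Φ(−2.645) = 0.4% | Φ(−2.282) = 1.1% |

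If the limit is instead the lower end of a two-sided 95% interval (z = 1.960), the no-effect figure is 97.5%.

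**Step 3: the same in PASI points.** The documents give no SD, so these are assumptions: an observed difference of −4 points, 27 per arm, SE = SD × √(2/27), one-sided 95% limits −4 ± 1.645 × SE.

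| SD | SE | Lower limit | Upper limit |
|---|---|---|---|
| 4 | 1.09 | −5.79 | −2.21 |
| 6 | 1.63 | −6.69 | −1.31 |
| 8 | 2.18 | −7.58 | −0.42 |

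As the data become noisier, the planned lower limit moves further below zero and so looks more favourable, while the upper limit correctly moves towards zero. With an observed difference of 0 and SD 6, the lower limit is still −2.69.

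**Step 4: the code against the text.** PROC MIXED requires the REPEATED effect to be made of classification variables. `week` is not in CLASS, so the printed step should stop; this is read from the syntax, and the code was not run in SAS. If the error were cleared without declaring `week` in CLASS, `week` would enter MODEL as a number:

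- The arm difference at week w would be w × (slope on PRCL − slope on placebo), that is, w/12 of the Week 12 difference: 1/12 = 8%, 2/12 = 17%, 4/12 = 33% and 8/12 = 67% at Weeks 1, 2, 4 and 8.
- The fixed part would have 1 intercept + 1 baseline slope + 3 arm slopes = 5 parameters.
- With `week` in CLASS it has 5 baseline slopes + 5 × 3 = 15 visit-by-arm means, so rank 20 (the intercept is absorbed by the 15 means).

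A numerical check of the design matrix for 81 patients, 3 arms and 5 visits gave ranks 5 and 20. Only the second is the model the text describes.

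**The case against.** **The sign of change is not defined.** If change were coded as improvement, the lower limit would be correct. That is true, and the wrong-side conclusion is conditional on it. But the SAP gives no such coding, the sentence speaks of a difference in mean scores, and post minus baseline is the usual convention. Either way the sign has to be stated.

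**The endpoints are inferred.** SAP 5.3 calls them secondary, whereas the SAP's secondary endpoints are adverse events and PK. Continuous PASI and sPGA are the only reasonable reading, but the label is another loose end in the paragraph.

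**The code is only an example.** It contains no statement that would produce the least squares means or the limit, so it must be completed anyway, and SAP 2.1 requires independent programming. A step that stops also cannot silently bias a result, so the continuous-week figures describe a possible bad repair and not the program as printed. This stands, and it makes the code point the smaller one. Validation would not correct the limit, because both programmers would follow the same sentence.

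**Other displays remain.** Analysis-of-variance comparisons, the model estimate and plots of least squares means with standard errors let a reader judge direction and approximate precision. No decision rule uses this limit. This holds the consequence down but does not supply the right limit.

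**The 2.12 SE benefit is borrowed.** It is an illustration and not a planned effect on mean change. The no-effect figures do not depend on it.

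**The 95% level is a choice.** Protocol 10.3.1 governs tests, the SAP takes precedence, and an exploratory limit need not match the primary one. This stands: the level is an unexplained inconsistency, not an error.

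**Conclusion.** The concern holds. With change taken as post minus baseline, SAP 5.3 reports the limit that cannot exclude no benefit, and its sign does little to separate an effective drug from an ineffective one. The code and the text in the same section disagree about the visit variable, and that part depends on no sign convention.

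The sizes rest on a normal approximation, and the point-scale example also rests on assumed SDs of 4 to 8. The effect is confined to an exploratory result. It should be corrected, but it does not threaten the trial's main conclusion.

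**What to change.** - In SAP 5.3, report the upper confidence limit for PRCL minus placebo in change from baseline (post minus baseline), or define improvement as baseline minus post and keep the lower limit. State the sign explicitly.
- State whether the limit is one-sided. Either use 90%, in line with SAP 5.1 and Protocol 10.3.1, or give the reason for 95%.
- Use one visit variable in CLASS, MODEL and REPEATED, for example `class week treatment patient;`, so that both interaction terms are visit-specific.

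The cost is one sentence of text and one word of code, with no change to data collection, sample size or the primary analysis. It is best made before unblinding, so that the choice of side cannot look data-driven.
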